ng/ml), and during pregnancy (9 to 200 ng/ml) (30). Progesterone and its metabolites interact with multiple neurotransmitter receptors including GABAA, glycine, sigma1, kainate, serotonin3, and nicotinic receptors (31). Among these actions, the best studied are the effects of progesterone on the GABA receptors. Progesterone's active metabolites, pregnanolone and allopregnanolone, have positive modulatory effects on GABAA receptors, and enhance GABA transmission (31). This may lead to reduced nicotine reward given the inhibitory actions of GABA on dopamine release in nucleus accumbens, a key step in mediating reward (32).

*Endogenous progesterone modulates nicotine addiction:* Many preclinical studies demonstrate that progesterone administration reduces the rewarding effects of cocaine (33, 34). Although the actions of exogenous progesterone on nicotine reward have not been assessed (27), Lynch (35) showed that in adolescent rats that are trained to self-administer nicotine, levels of responding under a progressive-ratio schedule are negatively associated with plasma progesterone levels. These results support an inhibitory influence of progesterone on nicotine self-administration.

In a human laboratory study using an ad lib smoking paradigm in female smokers, a lower progesterone to estrogen ratio was associated with greater number of puffs and increased puff intensity (36). Similarly, in a clinical trial, Allen et al. (4) randomized 200 women to quit in follicular or luteal phase of the menstrual cycle. Women who quit in the follicular phase relapsed faster to smoking than those who quit during the progesterone dominant luteal phase ((OR) = 2.87, 95% CI= 1.47– 5.59). The effect was robust; at 30 days the odds of remaining abstinent for the luteal phase group was 3.18 (95% CI= 1.59–6.34) higher than the follicular phase group. This same group showed that abstinence during the luteal phase of the cycle was accompanied by increases in allopregnanolone.(37) Mazure et al. (38) produced similar findings using bupropion. However, there are divergent findings (39, 40) that may be a result of differing study methods. Our proposed study will help clarify the literature by providing exogenous progesterone rather than relying on timing of the menstrual cycle to infer hormone levels.

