#### *Human subjects*

**Recruitment:** Recruitment will take place over 1.5 years, requiring enrollment of approximately 2-3 subjects per month. In our previous studies, we have been able to recruit on average 4 female smokers per month. Recruitment is further explained in Human Subjects but will be accomplished by direct screening in our reproductive health centers (20% of women seen for services in these centers are smokers), direct mail invitations, posters and flyers placed in local obstetrician-gynecologist offices. We have successfully used these techniques to recruit substance users, smokers and women with premenstrual dysphoric disorder in prior clinical trials. [name] has a secondary appointment in Obstetrics & Gynecology and has conducted numerous studies that entailed screening women in the reproductive health settings of Yale New Haven Hospital and their faculty (see Biosketch).

Update June 2017: All participants had blood levels of progesterone drawn. We were blind to assignment of participants but at the end of the study found that those who were randomized to active progesterone had low progesterone levels. This could be due to the progesterone preparation or the fact that smokers metabolize it very quickly. In any case, the low progesterone levels in the active treatment group obviates our ability to test our hypothesis that progesterone augmentation assists abstinence for smokers. Given the lack of funds, we cannot repeat the project. Rather, we are recruiting a second cohort and are using a commercially available oral micronized progesterone rather than the previous medication that was compounded for the study. We plan to enroll a minimum of 12 people with an imbalanced ratio of 6 active to 1 placebo. We will continue to obtain plasma levels of progesterone. This will enhance our ability to test our hypothesis. If need be in a final analysis, and give that this is a pilot project, we may be able to use the participants randomized to placebo in the first cohort and second cohort and the participants randomized to active in the second cohort.

Update September 2017: We request an additional blood draw (timeline is around Visit #6 or #7 to confirm progesterone plasma levels and compliance with pill taking. The second blood draw will be the same as the first one, completed at a professional lab on the first floor of the research site building. Approximately 6 ccs of blood will be drawn for each.

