pattern mixture models (26) and perform sensitivity analyses. In sensitivity analyses, participants who miss visits will be coded as smoking. Exploratory analysis will include plasma estradiol and progesterone levels as covariates in order to determine if they contribute to treatment response and PANAS scores as mediators of response to progesterone or placebo. Secondary analyses (the MNWS QSU-B) will be modelled similarly. The main outcome measures for the Stroop test are throughput and interference score. For the SST, the main outcomes are stop signal reaction time (msec) and go reaction time (msec). We will use hierarchical linear models with each cognitive measure as separate longitudinal outcomes and treatment group assignment as regressors.

**Power:** The sample size of 25 per condition was selected to provide an adequate assessment of feasibility and estimate effect sizes. Nonetheless, we determined what level of power we would have based upon a significance level of  $p < 0.05$ , 2 sided test for 7-day or prolonged abstinence. If rates of abstinence are 0.2 in the TNP only group and 0.4 in the progesterone and TNP group then the power would be 88%. If the rate of abstinence in the treated group is 0.38, power is reduced to 80%. In prior studies with the Stroop and SST, we found effect sizes  $> 0.5$  of progesterone vs placebo. Our sample size would have adequate power ( $> 80\%$ ) to detect a 2-fold difference in response. Clearly, these are large differences between groups but would provide a stable effect size estimate for a larger trial if findings are suggestive of a therapeutic effect of the combination treatment.

**Timeline:** We will use the first 3 months for study set up that will include final human subjects' approval, hiring and training of staff, database set up, computerization of the interview and assessment measures. Recruitment will begin immediately afterward. We will conduct ongoing data cleaning and will prepare reports for the human subjects' board, the DSMB and NCI at regular intervals. The final analysis and study report will occur in the last 3 months of the work period.

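### The plan says 25 women per arm would give a stable effect size for a larger trial, but at its own rates the 95% interval at one time point is about ±25 percentage points, and using the estimate only when results look suggestive biases it upward.

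*Combined protocol and SAP*

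**What the plan says.** All of this stands in the Power paragraph of Section V, item 12 (Statistical Considerations), unless noted.

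- Reason for the sample size: "The sample size of 25 per condition was selected to provide an adequate assessment of feasibility and estimate effect sizes".
- Test: significance level 0.05, two-sided, applied to either abstinence outcome.
- The main power statement reads: "If rates of abstinence are 0.2 in the TNP only group and 0.4 in the progesterone and TNP group then the power would be 88" percent.
- A second statement lowers the treated-group rate to 0.38 and puts power at 80%.
- The closing sentence concedes that these are large differences but says they "would provide a stable effect size estimate for a larger trial if findings are suggestive of a therapeutic effect".

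The paragraph gives no standard error, interval width or precision target. It does not say what counts as suggestive or how the larger trial would be sized.

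The June 2017 update (Section V, item 3, Human subjects; repeated in Section VI.A.2) adds a second cohort: "We plan to enroll a minimum of 12 people with an imbalanced ratio of 6 active to 1 placebo". It says that a final analysis might, if needed, compare second-cohort active women with placebo women from both cohorts. The precision sentence was not revised to match.

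**The concern.** Estimating an effect size is one of the two stated reasons for 25 per arm, so precision is a property that the plan claims for the design. Two things count against the claim.

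First, 25 per arm is few for a difference between two proportions, and nothing in the plan shows that the resulting interval is narrow enough to plan from.

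Second, the sentence attaches the estimate's use to a favourable result. Chance highs pass such a filter more often than chance lows, so an estimate that has passed it is too large on average, even when the unfiltered estimate is unbiased.

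At stake is the next trial. If the filtered estimate were taken as the effect to be detected, that trial would be too small.

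**Working it through.** **Inputs from the plan.** n = 25 per arm; two-sided alpha 0.05; abstinence 0.20 (patch only) vs 0.40 or 0.38 (progesterone plus patch).

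**The plan's own figures.** The paragraph has no precision figure, only powers. For 0.20 vs 0.40 the pooled-variance z-test gives power = Φ[(0.20 - 1.96·√(2·0.30·0.70/25)) / √(0.16/25 + 0.24/25)] = Φ[(0.200 - 0.254)/0.1265] = 33.5%, against the stated 88%. For 0.20 vs 0.38 it gives 28.5%, against the stated 80%. That is a separate defect. Correcting it would leave the precision sentence untouched.

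**Precision at one time point.**
- SE = √(0.2·0.8/25 + 0.4·0.6/25) = 0.1265. Half-width = 1.96 × 0.1265 = 0.248.
- Interval around 20 points: -4.8 to +44.8 (Wald). The Newcombe score interval is -5.3 to +42.3.
- For 0.20 vs 0.38 the half-width is 24.7 points.
- Risk ratio 2.0, 95% CI 0.80 to 5.02. Odds ratio 2.67, SE of the log = √(1/5 + 1/20 + 1/10 + 1/15) = 0.645, CI 0.75 to 9.45.

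**Effect of repeated visits.** Item 12 plans a GEE with an autoregressive correlation and gives no value for it. For an average over 8 weekly observations, the single-visit variance is multiplied by f = (1/8)·[1 + 2·Σ(1 - k/8)·ρ^k], k = 1 to 7. Assumed values of ρ give:

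| ρ (assumed) | f | Half-width (points) |
|---|---|---|
| 0.5 | 0.313 | 14 |
| 0.7 | 0.479 | 17 |
| 0.9 | 0.773 | 22 |

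**Selection.** I enumerated both Binomial(25) arms exactly at 0.20 vs 0.40 and took the mean observed difference among results that pass each candidate meaning of suggestive. I then sized a next trial for 80% power on that mean, holding control at 0.20: n per arm = (1.96 + 0.842)²·(p0·q0 + p1·q1)/d². For the true 20 points this is 7.85 × 0.40/0.04 = 78.5, so 79. The last column is the power of the trial so sized (n rounded up) when the truth is 20 points, by the unpooled z formula.

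| Meaning of suggestive (favouring progesterone) | Mean observed difference | Inflation | n per arm before rounding up | Power at true 20 points |
|---|---|---|---|---|
| two-sided p<0.05, Fisher | 36.5 points | 83% | 23.9 | 34% |
| two-sided p<0.05, chi-square | 33.2 | 66% | 29.1 | 41% |
| two-sided p<0.10 | 30.8 | 54% | 33.9 | 45% |
| two-sided p<0.20 | 28.1 | 40% | 40.8 | 53% |
| difference at least 10 points | 24.7 | 24% | 52.3 | 63% |
| any positive difference | 22.0 | 10% | 65.4 | 73% |

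A smaller true effect makes the inflation larger. At the plan's 0.20 vs 0.38, p<0.05 gives 80% (chi-square) or 99% (Fisher). At 0.20 vs 0.30 (my assumption) it is about 53% for any positive difference and 194% for p<0.05 (chi-square).

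**The possible 2017 comparison.** Twelve women at 6:1 is about 10 active and 2 placebo. If the first cohort supplied a full 25 placebo women, the comparison is 10 vs 27: SE = √(0.24/10 + 0.16/27) = 0.173, half-width 34 points. With only 20 placebo women it is 1.96·√(0.24/10 + 0.16/20) = 35 points. If the second cohort reached 21 (18 active and 3 placebo, so 18 vs 28), it is 1.96·√(0.24/18 + 0.16/28) = 27 points.

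**The case against.** **The planned analysis uses repeated visits, so ±25 may be too wide.** This stands as a limit on the figure. A time-averaged effect could be estimated to about ±14 to ±22 points under the correlations assumed above. But the paragraph states its rates as simple abstinence proportions, the Specific Aims place the outcomes at end of treatment and at 1 and 3 months, and no correlation is given. One time point is the fair default and should be labelled as such. Dropout, which the paragraph does not mention, would widen the interval.

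**Suggestive need not mean significant.** This also stands. A reader might infer that the estimate is bound to be inflated by two thirds or more and the next trial cut to about a third of the size needed. The documents do not support that: it requires two-sided p<0.05, and the word ordinarily means something weaker. At 0.20 vs 0.40 the looser rules give 10% to 54%. What survives is the direction, which is upward under every rule.

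**The plan never says the next trial will be sized on the observed estimate.** True. A reader might infer that the next trial would probably fail, but that follows only if the point estimate is used alone and the selection is strict or the true effect is smaller than planned. The condition can also be read as a reasonable test for whether to proceed at all. It need not be deleted.

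**An effect size is not the pilot's only product.** Agreed. Feasibility is named first, and the Statement of Purpose sets out a hypothesis test.

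**The ±34 points rests on assumed counts.** Agreed. The update gives 12 as a minimum, offers the pooled comparison only as a possibility, and does not say how many first-cohort women received placebo.

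**Conclusion.** The point holds as a claim about precision that the design does not meet. At the plan's own 0.20 vs 0.40, 25 per arm estimates the difference at one time point to about ±25 points, an interval from about -5 to +45. That is not a stable basis for planning.

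The selection effect is real, but its size depends on an undefined word. At those rates it ranges from about 10% (any positive difference) to 66% (p<0.05, chi-square) or 83% (Fisher), and is larger if the true effect is smaller. Under the chi-square and difference-based rules, a trial sized for 80% power on the selected mean would have about 29 to 65 per arm, against 79 for a true 20 points; the Fisher rule gives about 24. In every case power falls short of 80%.

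These figures assume complete data, a single time point, control abstinence of 0.20 and, for the sizing, sole reliance on the observed estimate. The plan neither commits to that last step nor rules it out.

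**What to change.** In the Power paragraph of Section V, item 12:

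1. Replace the word stable with a statement such as: 25 per arm estimates the difference in abstinence at one time point with a 95% confidence interval of about ±25 percentage points. If a narrower interval is claimed for a time-averaged GEE estimate, give the correlation assumed.
2. State that the estimate and its interval are reported whatever the result.
3. Keep the suggestive condition, if wanted, as the condition for proceeding to a larger trial, and define it. Add that the observed point estimate, selected on that condition, will not by itself size that trial. A stated minimum worthwhile difference or a lower confidence limit is one way to do so.
4. If the 2017 comparison is used, give its half-width with the counts assumed, for example about ±34 points for 10 active vs 27 placebo.

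The change is to wording only and adds no participants. Its cost is that the plan states a less favourable property for the design.

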## SECTION VI: RESEARCH INVOLVING DRUGS, BIOLOGICS, RADIOTRACERS, PLACEBOS AND DEVICES

*If this section (or one of its parts, A or B) is not applicable, state N/A and delete the rest of the section.*

### A. DRUGS, BIOLOGICS and RADIOTRACERS

1. **Identification of Drug, Biologic or Radiotracer:** What is (are) the **name(s)** of the drug(s) biologic(s) or radiotracer(s) being used? Identify whether FDA approval has been granted and for what indication(s).

All protocols which utilize a drug, biologic or radiotracer **not** approved by, but regulated by, the FDA, or a radiotracer regulated by the RDRC, must provide the following information:

- a. What is the Investigational New Drug (IND) **number** assigned by the FDA? We will not be applying for an IND.
- b. Who holds the IND? Multiple companies since the compound is generic.
- c. All protocols which utilize a radiotracer not approved by, but regulated by the FDA must provide the IND number: \_\_\_\_\_

Alternatively, use of the investigational radiotracer may be under RDRC/RSC oversight: (check if appropriate) \_\_\_\_\_

For all investigational radiotracers, attach a copy of the RDRC/RSC application (for radioisotopes used in the PET Center, PET Center personnel may complete this step) Go to <http://rsc.med.yale.edu/login.asp?url=myApps.asp>. When you have logged in, complete the application and attach a copy to this submission.

Alternatively, an **exemption from IND filing requirements** may be sought for a clinical investigation of a drug product that is lawfully marketed in the United States. If there is no IND and an exemption is being sought, review the following categories and complete the category that applies (*and delete the inapplicable categories*):

### Exempt Category 1

The clinical investigation of a drug product that is lawfully marketed in the United States can be exempt from IND regulations if all of the following are yes:

- i. The intention of the investigation is NOT to report to the FDA as a well-controlled study in support of a new indication for use or to be used to support any other significant change in the labeling for the drug. X Yes  No
  - ii. The drug that is undergoing investigation is lawfully marketed as a prescription drug product, and the intention of the investigation is NOT to support a significant change in the advertising for the product. X Yes  No
  - iii. The investigation does NOT involve a route of administration or dosage level or use in populations or other factor that significantly increases the risks (or decreases the acceptability of the risks) associated with the use of the drug product. X Yes  No
  - iv. The investigation will be conducted in compliance with the requirements for institutional (HIC) review and with the requirements for informed consent of the FDA regulations (21 CFR Part 50 and 21 CFR Part 56). X Yes  No
  - v. The investigation will be conducted in compliance with the requirements regarding promotion and charging for investigational drugs. X Yes  No
2. **Background Information:** Provide a description of previous human use, known risks, and data addressing dosage(s), interval(s), route(s) of administration, and any other factors that might influence risks. If this is the first time this drug is being administered to humans, include relevant data on animal models.

1) Progesterone: Progesterone, a natural hormone, is safe and well-tolerated by women. The safety, tolerability and efficacy of micronized progesterone is well established and it is FDA approved for hormone replacement therapy (HRT), absence of menstrual periods (amenorrhea), endometriosis, infertility treatment and preterm delivery. The recommended dose of progesterone for hormone replacement treatment is 200 to 400 mg/day, given as a single evening dose. After oral administration, micronized progesterone reaches its peak plasma levels in two to three hours and has an elimination half-life of three to four hours (18). Because of its short half-life progesterone will be given twice daily to maintain stable plasma levels. Progesterone doses higher than 400 mg/day will not be used since they are more likely to cause sedation. The safety and tolerability of micronized progesterone are well established.

Update June 2017: All participants had blood levels of progesterone drawn. We were blind to assignment of participants but at the end of the study found that those who were randomized to active progesterone had low progesterone levels. This could be due to the progesterone preparation or the fact that smokers metabolize it very quickly. In any case, the low progesterone levels in the active treatment group obviates our ability to test our hypothesis that progesterone augmentation assists abstinence for smokers. Given the lack of funds, we cannot repeat the project. Rather, we are recruiting a second cohort and are using a commercially available oral micronized progesterone rather than the previous medication that was compounded for the study. We plan to enroll a minimum of 12 people with an imbalanced ratio of 6 active to 1 placebo.

We will continue to obtain plasma levels of progesterone. This will enhance our ability to test our hypothesis. If need be in a final analysis, and give that this is a pilot project, we may be able to use the participants randomized to placebo in the first cohort and second cohort and the participants randomized to active in the second cohort.

2) Transdermal Nicotine Patch (TNP): TNP is currently available as an over the counter medication as an aid for smoking cessation. Consistent with the clinical guideline, participants who smoke more than 10 cigarettes per day will receive the following dose of TNP: 21mg/24 hours for 4 weeks, 14mg for weeks 5 and 6 and 7 mg for weeks 7 and 8. Participants who smoke between 5-10 cigarettes per day will receive the following dose of TNP: 14mg/24 hours for 6 weeks, 7mg for weeks 7 and 8. Neither longer term (> 8 weeks) nor a higher dose (> 21 mg/d) of nicotine patch improves efficacy over the standard treatment. Adverse effects of TNP include skin irritation, nausea, vomiting, sweating, mood and sleep disturbances. To avoid skin irritation, participants will be instructed to place a new patch on a relatively hairless location, typically between the neck and waist at the start of each day and to rotate the site of application. Smokers who experience sleep disturbances will be instructed to remove the patch before bedtime.

3. **Source:** a) Identify the source of the drug or biologic to be used.  
Banner Pharmacaps.

b) Is the drug provided free of charge to subjects?  Yes  No

If yes, by whom? The medication is provided free of charge to the subjects, but is paid for by the grant supporting this research.

4. **Storage, Preparation and Use:** Describe the method of storage, preparation, stability information, and for parenteral products, method of sterilization and method of testing sterility and pyrogenicity.

Check applicable Investigational Drug Service utilized:

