#### *Overview of the study design*

This will be a double-blind, placebo-controlled, pilot, randomized clinical trial. A total of 50 women who have regular menstrual cycles will be randomized to either progesterone (200 mgs BID) + Transdermal Nicotine Patch (TNP; 21 or 14 mg/day) or placebo + TNP (21 mg or 14mg/day) for 8 weeks. TNP will be tapered after 4-6 weeks as recommended by the Clinical Practice Guidelines for treating tobacco dependence (9). Participants who smoke more than 10 cigarettes per day will receive the following dose of TNP: 21mg/24 hours for 4 weeks, 14mg for weeks 5 and 6 and 7 mg for weeks 7 and 8. Participants who smoke between 5-10 cigarettes per day will receive the following dose of TNP: 14mg/24 hours for 6 weeks, 7mg for weeks 7 and 8.

Study medications will be discontinued at the end of Week 8. All participants will also be provided behavioral treatment for smoking cessation. Participants will be inducted onto progesterone (or placebo) + TNP over a one-week period (Week 1) during the mid luteal phase, within a week before menses and the target quit date will be set for the 5 (+/-2) days after onset of menses. Participants will have post-trial follow-up visits at 1 and 3 months following the end of the trial. The main study outcomes will be self-report of smoking abstinence, biochemically verified smoking abstinence, measures of cigarette craving and nicotine withdrawal, and measures of response inhibition.

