Determination of Eligibility and Baseline Visit: This interview will occur between estimated days 18-24 of the typical menstrual cycle. This will be a 120 minute visit. It will be broken down into two parts: 1) we will determine eligibility for the randomized clinical trial (RCT) and 2) we will obtain baseline measures for those who are eligible. The first procedure will be obtaining informed consent (please see consent procedures below). In the process of consent, we will explain to the provisionally eligible participant that part of the visit will be to determine eligibility for the RCT. For determination of eligibility, women will complete the NIDA Quickscreen (10); DSM 5 psychosis screener and DSM 5 screener for major depressive disorder, panic disorder or post-traumatic stress disorder (PTSD; current). Any positive responses on these measures will trigger an evaluation, including the SCID and assessment by a study clinician (a physician for medical issues; a psychologist, physician or social worker if the issues is an exclusionary psychiatric diagnosis) that will indicate whether or not the participant is eligible; 2) a medical history will be gathered to obtain information on allergies, especially progesterone, use of medication, pregnancy planning, history of breast cancer, deep vein thrombosis, coagulation problems, liver failure, cervical intraepithelial neoplasm, allergy to nuts, etc; and 3) nicotine intake history including use of all nicotine products, number of cigarettes smoked and use of other nicotine products in the previous month, prior treatment for smoking cessation; prior intolerance or allergy to transdermal nicotine patch; 4) laboratory tests that include urine for pregnancy, cotinine and drugs of abuse and expired breath CO.

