The RA will complete a checklist that indicates eligibility criteria. The checklist will be reviewed by study clinician who will confirm that this information has been gathered and that the participant meets criteria for participation. For women who continue to be eligible, the RA and/or study clinician will ask baseline measures that include: 1) a menstrual history form including module for diagnosis of premenstrual dysphoric disorder and menstrual cycle dating, the Fagerstrom Test for Nicotine Dependence (FTND) (11); the Minnesotal Nicotine Withdrawal Scale (MNWS) (12), the Questionnaire on Smoking Urges-Brief (QSU-B) (13) and the Positive and Negative Affect Schedule(14) . They will also complete the following neurocognitive tasks: 1) the Stroop, (15) 2) Go/No Go, 3) Digit Symbol Substitution Test (part of the WAIS III), 4) The Shipley Institute of Living Scale (SILS) is a paper-and-pencil, self-administered scale that consists of a 40-item vocabulary and a 20-item pattern recognition section (16).

Randomization/Visit 1: After eligibility is confirmed and the baseline assessments are completed, women will be randomized. Women will then begin smoking cessation counseling and will receive two weeks supply of their study medication, TNP + either oral micronized progesterone or placebo. They will be instructed to apply one nicotine patch /day and to take one pill twice daily after the visit. They will be instructed to set a quit date for the 5 (+/-2) days after the onset of menses, ideally around the 3-4th day when perimenstrual symptoms have abated and before estrogen peaks. We will call them at the estimated time of menses onset to confirm dates and quit date plans. We used similar strategies in smoking studies and menstrual cycle studies (6).

Treatment Phase (Visit 2 to 8): Women will be seen for follow up around days 7-11 of their menstrual cycle, shortly after their quit date. This visit will confirm that treatment with TNP + progesterone or placebo was initiated and maintained for the estimated 2 weeks since Visit 1. Medication compliance will be assessed by pill count. Support and counseling will be

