|  Decisionally Impaired |  Employees                                    |  Pregnant women and/or fetuses           |
|  Yale Students         |  Females of childbearing potential |  |

NOTE: Is this research proposal designed to enroll children who are wards of the state as potential subjects?  Yes  No (If yes, see Instructions section VII #4 for further requirements)

7. **Inclusion/Exclusion Criteria:** What are the criteria used to determine subject inclusion or exclusion?

Inclusion criteria: a) Aged 18 - 45; b) smoking at least 5 cigarettes/ day for at least one year; c) regular menstrual cycles every 24–36 days for the previous 6 months; d) motivated to quit smoking (i.e., a rating of at least “7 “on a 10-point scale where 1 is not at all motivated and 10 is extremely motivated); e) in good health; and f) using an acceptable, non-hormonal birth control.

Exclusion criteria: a) a history of major medical illnesses including liver diseases, heart disease, diabetes, malignancy including history of breast cancer, deep vein thrombosis, blood coagulation problems including a history or family history of thrombophilia, use of an antithrombotic agent, liver failure, cervical intra-epithelial lesions III or greater that are untreated, allergy to peanuts or other nuts, or other medical conditions that the physician investigators deems will make study participation unsafe for the subject; b) current or past history bipolar disorder or schizophrenia or current diagnosis of major depression, panic disorder or post-traumatic stress disorder; c) use of all non-nicotine drug substances are excluded at the mild DSM-V diagnosis; alcohol use is excluded at the moderate DSM-V level diagnosis (caffeine use is not evaluated or excluded); d) currently undergoing treatment with another pharmacological agent for smoking cessation; e) daily use of sedating medications including sleeping aids and others; f) use of nicotine from cigars, pipes, chewing tobacco, e-cigarettes; g) pregnant, breast- feeding or intending to become pregnant within 6 months

and; h) allergy to nicotine patch or progesterone.

8. How will **eligibility** be determined, and by whom?

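### Cohort 1's low progesterone readings do not by themselves show a failed product, fast metabolism or an untestable hypothesis, because the schedule lets capsules run out before the first blood draw

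*Combined protocol and SAP*

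**What the plan says.** The June 2017 update appears in Section V (Research Plan, Human subjects) and again in Section VI.A, item 2. It reports that women randomised to active progesterone in cohort 1 were found at the end of the study to have low levels. On the cause it says: "This could be due to the progesterone preparation or the fact that smokers metabolize it very quickly". It continues that, regardless, "the low progesterone levels in the active treatment group obviates our ability to test our hypothesis". A second cohort then receives a commercial product at a 6:1 ratio. If needed, the final analysis may compare cohort 2's active women with placebo women from both cohorts, leaving out cohort 1's active arm.

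The schedule is in Section V:

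- **Baseline visit:** "This interview will occur between estimated days 18-24 of the typical menstrual cycle".
- **Visit 1:** women "will receive two weeks supply of their study medication, TNP + either oral micronized progesterone or placebo", one capsule twice daily.
- **Visit 2:** "Women will be seen for follow up around days 7-11 of their menstrual cycle, shortly after their quit date". The same paragraph expects about two weeks since Visit 1 and calls for a pill count.
- **First blood draw:** around Visit 2.
- **Eligible cycles:** "regular menstrual cycles every 24–36 days for the previous 6 months".
- **Overview of the study design:** induction is "during the mid luteal phase, within a week before menses".
- **Strategies to protect the blind:** participants attend weekly for dispensing.

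The September 2017 update adds a draw around Visit 6 or 7 "to confirm progesterone plasma levels and compliance with pill taking".

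**The concern.** The update considers what the product or the body did with the drug. It does not consider whether the woman still had capsules, was taking them, or was sampled long after a dose. It mentions no pill count, dispensing date or time since dose, and gives neither the measured values nor a cut-off for low. The schedule makes these omissions matter: the first draw falls in the early part of a cycle, when the Background section puts natural progesterone below 1 ng/ml, so a woman without recent drug on board would read low on any product.

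Three things are at stake. The report could state that the compounded product failed, or that smokers clear progesterone too fast, when neither is shown. If the cause was supply or adherence, a new product does not address it, and cohort 2's first draw keeps the same timing. And the permitted fallback analysis replaces a randomised comparison for Aim 1 with one that is not randomised, chosen after levels were seen by arm.

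**Working it through.** **Inputs.** Start day d1 = 18 to 24 (baseline visit, with Visit 1 taken as the same day, an assumption). Visit 2 day d2 = 7 to 11 of the next cycle. Cycle length L = 24 to 36. Supply = 14 days. Half-life = 3 to 4 hours (Section VI.A, item 2).

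**Gap from Visit 1 to the draw** = L − d1 + d2.

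- Shortest: 24 − 24 + 7 = 7 days. Longest: 36 − 18 + 11 = 29 days.

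**The plan's own figure.** The expected two weeks is recovered only as a centre. For a 28-day cycle with at most 7 days of the cycle left at the start (d1 = 21 to 24), gaps run 11 to 18 days with mean 14.5. Without that limit the mean is 16 days for a 28-day cycle and 18 days over all cycle lengths.

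**Share of gaps over 14 days**, counting every whole-day combination as equally likely, with no resupply before the draw:

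| Assumption | Count | Share |
|---|---|---|
| All windows, cycles 24–36 | 346 of 455 | 76% |
| 28-day cycle | 25 of 35 | 71% |
| 24-day cycle, or start on any of the 7 days before menses | 6 of 35 | 17% |
| All windows, at most 7 days of the cycle left at start | 66 of 175 | 38% |
| 28-day cycle, at most 7 days left | 10 of 20 | 50% |
| Visit 2 booked at 14 days | – | near 0 |

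The last-week limit is sensitive to how days are counted. Allowing at most 6 days left gives 38 of 140 (27%) over all cycles and 6 of 15 (40%) at 28 days.

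The two start rules also cannot always be met together. In a 32-day cycle, day 24 still leaves 32 − 24 = 8 days, so no start on days 18 to 24 falls within a week of menses.

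**Level remaining** after t hours, by simple exponential decay that ignores absorption time = 2^(−t/half-life).

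- 12 hours: 2^(−12/3) = 6.25% to 2^(−12/4) = 12.5%.
- 24 hours: 2^(−24/3) = 0.4% to 2^(−24/4) = 1.6%.

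So a woman one day past run-out reads close to her own baseline whatever the product. A supplied, adherent woman sampled at the end of a 12-hour interval can also read low.

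**Why the pill count alone does not settle it.** Fourteen days at two capsules a day is 28 capsules. A woman seen on day 18 with none left looks fully compliant, yet would have been without drug for about four days. The count needs the dispensing and draw dates beside it.

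**The case against.** The strongest reply is that the decision does not depend on the cause. The update words the causes tentatively and says the hypothesis is untestable whichever applies: if active women had little progesterone, the arm could not test its effect. This stands in part. If exposure was low throughout treatment for any reason, cohort 1 says little about the pharmacological hypothesis. But a reading around Visit 2 does not show low exposure over 8 weeks, and the comparison by randomised assignment remains valid and reportable.

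Other points also stand. Weekly dispensing could mean that women were resupplied before the draw, although this conflicts with the two-week supply at Visit 1. Cohort 1's draw time is inferred from text that already carries the September 2017 change. The Visit 2 pill count and the later second draw give some protection, the latter mainly to cohort 2. The fallback analysis is permitted, not fixed.

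A reader might infer that most women were out of capsules when sampled. The documents do not support that. The 76% treats all days as equally likely and ignores the last-week start limit, and none of the shares is an observed frequency. A reader might also infer that the sponsor has asserted product failure or has already discarded the arm; the text says only that these causes are possible and that such an analysis may be used.

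**Conclusion.** The point holds as a gap in inference. The schedule in the current text allows run-out before the first draw, and the half-life allows late sampling to look the same. The update excludes neither, nor missed doses. It therefore does not establish product failure, fast metabolism, or that cohort 1 cannot address the hypothesis.

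The size is conditional. Gaps over 14 days make up about 17% to 76% of combinations if days are equally likely, Visit 1 is on the baseline day and no capsules are supplied before the draw. The share is about 38% (50% for a 28-day cycle) if the last-week start limit also applies, and near zero if visits were booked at two weeks. Run-out is shown to be possible, not to have occurred.

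**What to change.** 1. From data already held, tabulate cohort 1 active-arm levels by days from last dispensing to draw, Visit 2 pill count and, where recorded, hours since last dose. Read cohort 2's levels the same way.
2. In both places where the June 2017 update appears, add run-out, non-adherence and time since dose as possible causes. State product failure or fast metabolism only if levels are low in women who were supplied, adherent and sampled soon enough after a dose.
3. Report cohort 1's randomised comparison for Aim 1 whatever the levels show, so that it does not hinge on a post-randomisation measurement seen after unblinding. Label any comparison of cohort 2 active women with pooled placebo as non-randomised and exploratory.
4. Reconcile the passages on start window, baseline visit, Visit 1 supply and weekly dispensing.

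The cost is one table from dispensing dates, draw dates and pill counts, plus revised wording. The downside is that the stated reason for cohort 2 may become weaker. If levels prove low in supplied, adherent, suitably timed women, the sponsor's explanation becomes stronger.
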